3.2.3 Documentation

Data including baseline clinical and procedural characteristics with all FFR values (pre- and post-PCI resting, dPR, contrast, and adenosine) will be entered into the electronic case report form (eCRF) and used to analyze the primary and secondary study endpoints. These data will be stored in the IBM Clinical Data platform mirroring the NCDR dataset.

The post-PCI (final) aFFR will be used for correlation to 1-year clinical outcomes of death, MI, and TVR. These clinical endpoints will be recorded during the index hospitalization (prior to discharge), 30-day visit (at the routine follow-up appointment or telephone call if this appointment is missed), and at 1 year by telephone. See post-procedure follow-up section for details on data acquisition and definitions.

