3.3.2 Secondary Endpoints

The secondary endpoint is the association between the final post-PCI aFFR and long-term clinical outcomes. The long-term clinical outcomes will include TVR and composite MACE (death, MI, and TVR) during the index hospitalization, 30 days, and 1 year.

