4.4 Withdrawal of Patients

Patients may voluntarily withdraw for any reason without penalty or loss of benefits to which they are entitled.

If a patient withdraws from the study at any time either at his or her request or at the investigator's discretion, the reasons for withdrawal must be recorded on the relevant page of the patient's eCRF. Patients who withdraw from the study prematurely should undergo all end-of-study assessments, if possible. Study site personnel should make every effort to prevent losing patients to follow-up.

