9.4 Secondary Endpoint Analysis

9.4.1 Assessment of the Relationship Between Post-Percutaneous Coronary Intervention Fractional Flow Reserves and Long-Term Clinical Outcomes

A logistic model will be developed that assesses whether there is a relationship between final PCI FFR (resting, dPR, cFFR, aFFR) and long-term outcomes (death, MI, TVR). The model will include the known covariates for predicting revascularization outcomes: stent length, vessel diameter, diabetes, history of cardiovascular disease, and multi-vessel disease.

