9.4.2 Additional Endpoints

Descriptive statistics will be provided for any additional endpoints. For binary measures, the rate and Clopper-Pearson 95% CI will be provided. For continuous endpoints, the mean, median, SD, and the interquartile range will be provided. For time to event measures, the Kaplan-Meier product limit estimate and 95% CI will be provided for each year of follow-up.

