9.4.3 Missing Data

If the missing data for the per-protocol population are less than 10%, no attempt will be made to impute the missing data. However, a tipping analysis will be performed as a sensitivity analysis. If the missing data are greater than 10%, based on the type of missing data (missing at random, not missing at random, missing completely at random, etc.), the appropriate multiple imputation method will be employed as a sensitivity analysis to assess the impact of the missing data on the primary endpoint.

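### The logistic model for final FFR and 1-year outcomes has no rule for patients whose 1-year status is unknown; a censored-data model would close the gap cheaply

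*Combined protocol and SAP*

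**What the plan says.** Section 9.4.1 names the model: "A logistic model will be developed that assesses whether there is a relationship between final PCI FFR" (resting, dPR, cFFR or aFFR) and death, MI and TVR, adjusted for five covariates. It states no time point and no rule for incomplete follow-up. The time points come from elsewhere. Section 3.2.3 says "The post-PCI (final) aFFR will be used for correlation to 1-year clinical outcomes of death, MI, and TVR", and section 3.3.2 says "The long-term clinical outcomes will include TVR and composite MACE (death, MI, and TVR) during the index hospitalization, 30 days, and 1 year".

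Follow-up can end early. Section 4.4 allows withdrawal at any time and adds: "Patients who withdraw from the study prematurely should undergo all end-of-study assessments, if possible". Table 1 puts the last contact at 1 year with a window of 30 days either side, so it may fall at day 335. Section 4.1 (criterion 4) asks for willingness to be contacted at 1 year together with a chart review for events. Section 6.5 has source documents collected to verify endpoints.

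On missing data, 9.4.3 says: "If the missing data for the per-protocol population are less than 10%, no attempt will be made to impute the missing data". A tipping analysis is added in that case, with no endpoint named. Above 10%, multiple imputation is a sensitivity analysis "to assess the impact of the missing data on the primary endpoint".

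Section 9.4.2 opens with "Descriptive statistics will be provided for any additional endpoints" and includes this line: "For time to event measures, the Kaplan-Meier product limit estimate and 95% CI will be provided for each year of follow-up". It defines no time-to-event endpoint, time origin or censoring rule.

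**The concern.** Consider a patient last known to be event-free at month 3. The 1-year status is unknown, and the logistic model has no place for partial follow-up. The patient can be left out, entered as event-free, or handled in some other way decided later, possibly after results are seen. The withdrawal visit in 4.4 makes the second route easy to take by accident, because an early end-of-study assessment can look like a 1-year status.

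The imputation in 9.4.3 does not help. The primary endpoint is measured during the procedure, so loss to follow-up does not touch it. The secondary endpoint, which does depend on follow-up, is not named there.

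At stake is the one model that answers the secondary objective. If loss differs by FFR level, for example because patients with a low final FFR are followed more closely, the handling chosen moves the estimated association.

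**Working it through.** **1. The plan's own figure.** The documents give no sample size, event rate or loss rate for the secondary analysis. The only sample-size figure is 208 pairs for the AUC test in 9.3.2. It reproduces with the binormal variance V: positives = (z0.975·√V(0.8) + z0.90·√V(0.9))² / 0.1² = 100.9, so 101; negatives = 101 × 1.06 = 107; total 208. Nothing below changes it.

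**2. Effect on the 1-year risk.** Assumptions: constant hazards, loss unrelated to FFR, and every event before loss captured. Let p be the true 1-year risk and d the loss, with λ = −ln(1−p) and μ = −ln(1−d).
- Observed events: O = λ/(λ+μ) × [1 − (1−p)(1−d)]
- Early status carried to 1 year: risk = O
- Lost patients dropped: risk = O / [O + (1−p)(1−d)]

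Example with p = 10%, d = 20%: λ = 0.1054, μ = 0.2231, (1−p)(1−d) = 0.72. Then O = 0.1054/0.3285 × 0.28 = 0.090, and the dropped version is 0.090/0.810 = 0.111.

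| True risk | Loss | Carried | Dropped |
|---|---|---|---|
| 10% | 5% | 9.8% | 10.2% |
| 10% | 10% | 9.5% | 10.5% |
| 10% | 15% | 9.2% | 10.8% |
| 10% | 20% | 9.0% | 11.1% |
| 20% | 20% | 18.0% | 22.0% |

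Under these assumptions Kaplan-Meier targets the true risk in every row.

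**3. Effect on the FFR coefficient.** Simulated unadjusted log odds ratio per SD of FFR. All rates and effect sizes are assumed.
- A: n = 200, 1-year risk 15%, log HR 0.5 per SD, 15% loss unrelated to FFR
- B: as A, but loss related to FFR
- C: base rate 0.12 per year, HR 1.8 per SD, 20% loss in the high-FFR half and 5% in the low half, events captured up to the time of loss
- D: C reversed
- E and F: C and D, but events seen only at the planned contacts (discharge, 30 days, 1 year)

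| Setting | Full data | Dropped | Carried |
|---|---|---|---|
| A | 0.570 | 0.570 (0%) | 0.566 (−0.7%) |
| B | 0.544 | 0.583 (+7.2%) | 0.473 (−13.1%) |
| C | 0.623 | 0.585 (−6.1%) | 0.650 (+4.3%) |
| D | 0.660 | 0.699 (+5.9%) | 0.618 (−6.4%) |
| E | 0.643 | 0.638 (−0.8%) | 0.700 (+8.9%) |
| F | 0.644 | 0.650 (+0.9%) | 0.558 (−13.4%) |

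Percentages are (value − full data)/full data. In B, Cox gave a log HR of 0.483 against the true 0.5 (−3.4%). In C to F it stays near the true ln 1.8 = 0.588.

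**4. Effect on power and type I error.** In B, power is 75% with full data, 75% dropped, 58% carried and 69% with Cox (simulation error about 2 points). In C and D with 97 patients, it ranges from 42% to 50% by handling, and Cox gives 45% in both. With no true effect and FFR-related loss (n = 200, risk 10%), rejection rates were 4.6% carried, 5.5% dropped and 4.8% Cox.

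**5. Contact window.** A call at day 335 leaves 30/365 = 8.2% of the year unseen unless the chart review covers it. If calls spread evenly over the window, half are early by 15 days on average: 0.5 × 15/365 = 2.1%.

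**6. Events available.** Five covariates plus one FFR index make six parameters. Section 1 quotes registry 6-month rates from 4.9% to 20.3%. At an assumed 5% to 20.3%, 200 patients give 10 to 41 events (1.7 to 6.8 per parameter). If only PCI patients count, 200/2.06 = 97 patients give 5 to 20 events (0.8 to 3.3 per parameter).

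**The case against.** The outcomes are defined at fixed times, and logistic regression of 1-year status is a standard choice when follow-up is nearly complete. The protocol works towards that: chart review in 4.1, source documents in 6.5, an instruction in 4.4 to avoid loss, and exclusion of patients with a life expectancy under 1 year. The tipping analysis in 9.4.3 sits under the secondary section and could be read to cover this endpoint. On the actual contact schedule, dropping lost patients biases the coefficient by under 1% (settings E and F). Precision also dwarfs the shift: with 97 patients the standard error is about 0.34, so a shift of 0.04, as in C and D, is about a tenth of it. Few events are the larger limit.

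Most of this stands, and it keeps the point modest. It does not supply the missing rule. The tipping analysis applies only below 10% missing and names no endpoint. Carrying early status forward, which nothing forbids, has the larger effect.

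Two stronger readings should be set aside. A reader might infer that the plan drops early leavers or counts them as event-free; no section says either. A reader might also infer from the Kaplan-Meier line in 9.4.2 that the plan already works with event times and censoring. That line is a general provision for unnamed additional endpoints, and censoring is never mentioned. Nor is counting a patient who dies without TVR as having no TVR an error in itself. It is a legitimate cumulative-risk target, but it has to be declared.

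**Conclusion.** The point holds as a gap in the main secondary analysis that should be closed. Section 9.4.1 fixes a model that needs 1-year status, and no section says what to do when that status is unknown. With loss that depends on FFR, the coefficient shifts by roughly 0 to 7% if such patients are dropped and about 4 to 13% if early status is carried forward. With loss that is low or unrelated to FFR, it barely moves. Type I error stayed near 5% in the case checked.

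These sizes rest on assumed loss rates, event risks and effect sizes, since the documents give none for this study. A Cox model removes the need for a known 1-year status, but it still assumes that censoring is non-informative given the covariates. It does not add events.

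**What to change.** In 9.4.1:
- Make the main analysis a Cox model, penalised if events are few, for time from index procedure to first MACE and to TVR.
- Censor event-free patients at the last known contact or chart review, or at day 365, whichever comes first.
- Treat death as a competing event for TVR: cause-specific hazard for the association, and cumulative incidence for TVR risk. One minus Kaplan-Meier with deaths censored would overstate TVR risk.
- Report Kaplan-Meier MACE risk at 30 days and 1 year.
- Keep the logistic model as supportive, and state that an early withdrawal assessment is not entered as 1-year status.

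In Table 1, set the final contact on or after day 365, or require the chart review to cover events through day 365.

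Cost: event and last-contact dates must be recorded, which the source documents in 6.5 probably allow. Proportional hazards must be checked, and some calls move a few weeks later. The 208 pairs for the primary test are unaffected.

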9.4.2 Additional Endpoints

Descriptive statistics will be provided for any additional endpoints. For binary measures, the rate and Clopper-Pearson 95% CI will be provided. For continuous endpoints, the mean, median, SD, and the interquartile range will be provided. For time to event measures, the Kaplan-Meier product limit estimate and 95% CI will be provided for each year of follow-up.

9.4.3 Missing Data

If the missing data for the per-protocol population are less than 10%, no attempt will be made to impute the missing data. However, a tipping analysis will be performed as a sensitivity analysis. If the missing data are greater than 10%, based on the type of missing data (missing at random, not missing at random, missing completely at random, etc.), the appropriate multiple imputation method will be employed as a sensitivity analysis to assess the impact of the missing data on the primary endpoint.

9.5 Estimated Duration of the Study

The estimated enrollment duration is approximately 1 year. It is estimated that the study involvement for all sites will extend approximately 1 year after the last entered subject's procedure.

10. STUDY ETHICAL CONSIDERATIONS

10.1 Confidentiality of Patients

Patient confidentiality will be maintained throughout the clinical study in a way that ensures the information can always be tracked back to the source data. For this purpose, a unique patient identification code will be used that allows identification of all data reported for each study patient.

Patient information collected in this study will comply with the standards for protection of privacy of individually identifiable health information as promulgated in the Health Insurance Portability and Accountability Act of 1996 (HIPAA). All records will be kept confidential, and the patient's name will not be released at any time. Patient records will not be released to anyone other than sponsor or its designees, and responsible regulatory authorities, when requested.

11. ADMINISTRATIVE PROCEDURES

11.1 Duke Clinical Research Institute Coordinating Center Responsibilities

11.1.1 Investigator Training

All Investigators and their study personnel will receive training regarding the study procedures. This training will take place prior to enrollment of the first patient at each study center. Any new personnel joining the study after initiation will receive the same training prior to participation.

Questions around eCRF completion or study procedures should be directed to the site's clinical research associate.

11.2 Investigator's Responsibilities

11.2.1 Reporting and Recording of Study Data

It is the investigator's responsibility to ensure the accuracy, completeness, and timeliness of the data reported on the patient's eCRF. Source documentation supporting the eCRF data should indicate the patient's participation in the study and should document the dates and details of study procedures and patient's clinical status from informed consent through the 1 year contact.

11.2.2 Source Documentation

The investigator must maintain adequate and accurate source documents upon which case reports for each patient are based. They are to be separate and distinct from eCRFs.

These records should include detailed notes on:

- The medical history prior to participation in the study
- The basic identifying information, such as demographics, that link the patient's source documents with the eCRF
- The results of all diagnostic tests performed, diagnoses made, therapy provided, and any other data on the condition of the patient
- The patient's exposure to study treatment
- The patient's exposure to any concomitant therapy (including date and quantity dispensed)
- All relevant observations and data on the condition of the patient throughout the study

- The oral and written communication with the patient regarding the study treatment (including the risks and benefits of the study)
- The date of informed consent recorded in the source documentation

11.2.3 Records Retention

The investigator must inform, and receive approval from, the Sponsor prior to the destruction of any documents, if documents are to be transferred to a different facility or transferred to a different owner.

The investigator shall maintain the records required for this investigation for a period of 6 years after the date on which the investigation is terminated or completed.

12. STEERING COMMITTEE, DATA AND SAFETY MONITORING COMMITTEE, AND ADJUDICATION COMMITTEE**12.1 Steering Committee**

The Steering Committee for this study will supervise the conduct, administration, and course of the clinical trial. They will provide scientific and clinical oversight and will meet periodically to monitor subject enrollment and overall study progress. This committee will also be responsible for reviewing the final results, determining the methods of presentation and publication, and selection of secondary projects and publications. The steering committee for this study will include the study chair, principal investigator, up to 2 additional clinicians experienced in FFR clinical trials, a DCRI statistician, and a member from the ACIST team.

12.2 Fractional Flow Reserve Core Lab

This purpose of the core lab will be to review the quality and validity of each FFR tracing obtained from all subjects enrolled in the study as well as derive the dPR via waveform analysis. The core lab will consist of 1 physician knowledgeable in FFR physiology and the catheter techniques employed for proper FFR acquisition and 1 engineer from the ACIST team with specific knowledge about FFR acquisition and data analysis from the NAVVUS RxI FFR system. These 2 members will perform an independent, blinded review of all FFR tracings and will make a recommendation for exclusion if any of the following criteria are noted: ventricularization of aortic waveform, change in dampening/distortion of aortic waveform, or significant signal drift. Discrepancies in recommendations will be resolved by joint review of the 2 members of the tracing in question.

13. POLICY FOR PUBLICATION AND PRESENTATION OF DATA

The sponsor will encourage the scientific publication of data from clinical research trials. However, investigators may not present or publish partial or complete study results individually. The principal investigators and the partners may propose appropriate scientific manuscripts or abstracts from the study data. Any manuscript or abstract proposed by the investigators must be reviewed and approved in writing by the Steering Committee before submission for publication.

